5.3.2 Eliciting Adverse Event Information

A consistent methodology of non-directive questioning should be adopted for eliciting adverse event information at all patient evaluation timepoints. Examples of non-directive questions include the following:

"How have you felt since your last clinic visit/ telephone call?"

"Have you had any new or changed health problems since you were last here/ we talked by the phone?"

5.3.3 Assessment of Severity of Adverse Events

The adverse event severity grading scale for the NCI CTCAE (v4.0) will be used for assessing adverse event severity. [Table 4](#) will be used for assessing severity for adverse events that are not specifically listed in the NCI CTCAE.

Table 4 Adverse Event Severity Grading Scale for Events Not Specifically Listed in NCI CTCAE

Grade	Severity
1	Mild; asymptomatic or mild symptoms; clinical or diagnostic observations only; or intervention not indicated
2	Moderate; minimal, local, or non-invasive intervention indicated; or limiting age-appropriate instrumental activities of daily living ^a
3	Severe or medically significant, but not immediately life-threatening; hospitalization or prolongation of hospitalization indicated; disabling; or limiting self-care activities of daily living ^{b,c}
4	Life-threatening consequences or urgent intervention indicated ^d
5	Death related to adverse event ^d

NCI CTCAE = National Cancer Institute Common Terminology Criteria for Adverse Events.

Note: Based on the most recent version of NCI CTCAE (v4.0), which can be found at: http://ctep.cancer.gov/protocolDevelopment/electronic_applications/ctc.htm

^a Instrumental activities of daily living refer to preparing meals, shopping for groceries or clothes, using the telephone, managing money, etc.

^b Examples of self-care activities of daily living include bathing, dressing and undressing, feeding oneself, using the toilet, and taking medications, as performed by patients who are not bedridden.

^c If an event is assessed as a "significant medical event," it must be reported as a serious adverse event (see [Section 5.4.2](#) for reporting instructions), per the definition of serious adverse event in [Section 5.2.2](#).

^d Grade 4 and 5 events must be reported as serious adverse events (see [Section 5.4.2](#) for reporting instructions), per the definition of serious adverse event in [Section 5.2.2](#).

5.3.4 Assessment of Causality of Adverse Events

Investigators should use their knowledge of the patient, the circumstances surrounding the event, and an evaluation of any potential alternative causes to determine whether an adverse event is considered to be related to the study drug, indicating "yes" or "no" accordingly. The following guidance should be taken into consideration (see also [Table 5](#)):

- Temporal relationship of event onset to the initiation of study drug
- Course of the event, with special consideration of the effects of dose reduction, discontinuation of study drug, or reintroduction of study drug (as applicable)
- Known association of the event with the study drug or with similar treatments
- Known association of the event with the disease under study

Pirfenidone—F. Hoffmann-La Roche Ltd

- Presence of risk factors in the patient or use of concomitant medications known to increase the occurrence of the event
- Presence of non-treatment-related factors that are known to be associated with the occurrence of the event

Table 5 Causal Attribution Guidance

Is the adverse event suspected to be caused by the study drug on the basis of facts, evidence, science-based rationales, and clinical judgment?	
YES	There is a plausible temporal relationship between the onset of the adverse event and administration of the study drug, and the adverse event cannot be readily explained by the patient's clinical state, intercurrent illness, or concomitant therapies; and/or the adverse event follows a known pattern of response to the study drug; and/or the adverse event abates or resolves upon discontinuation of the study drug or dose reduction and, if applicable, reappears upon re-challenge.
NO	An adverse event will be considered related, unless it fulfills the criteria specified below. Evidence exists that the adverse event has an etiology other than the study drug (e.g., preexisting medical condition, underlying disease, intercurrent illness, or concomitant medication); and/or the adverse event has no plausible temporal relationship to administration of the study drug (e.g., cancer diagnosed 2 days after first dose of study drug).

For patients receiving combination therapy, causality will be assessed individually for each protocol-mandated therapy.

5.3.5 Procedures for Recording Adverse Events

Investigators should use correct medical terminology/concepts when recording adverse events on the Adverse Event eCRF. Avoid colloquialisms and abbreviations.

Only one adverse event term should be recorded in the event field on the Adverse Event eCRF.

5.3.5.1 Diagnosis versus Signs and Symptoms

For adverse events, a diagnosis (if known) should be recorded on the Adverse Event eCRF rather than individual signs and symptoms (e.g., record only liver failure or hepatitis rather than jaundice and elevated transaminases). However, if a constellation of signs and/or symptoms cannot be medically characterized as a single diagnosis or syndrome at the time of reporting, each individual event should be recorded on the Adverse Event eCRF. If a diagnosis is subsequently established, all previously reported adverse events based on signs and symptoms should be nullified and replaced by one adverse event report based on the single diagnosis, with a starting date that corresponds to the starting date of the first symptom of the eventual diagnosis.

Pirfenidone—F. Hoffmann-La Roche Ltd

5.3.5.2 Adverse Events That Are Secondary to Other Events

In general, adverse events that are secondary to other events (e.g., cascade events or clinical sequelae) should be identified by their primary cause, with the exception of severe or serious secondary events. A medically significant secondary adverse event that is separated in time from the initiating event should be recorded as an independent event on the Adverse Event eCRF. For example:

- If vomiting results in mild dehydration with no additional treatment in a healthy adult, only vomiting should be reported on the eCRF.
- If vomiting results in severe dehydration, both events should be reported separately on the eCRF.
- If a severe gastrointestinal hemorrhage leads to renal failure, both events should be reported separately on the eCRF.
- If dizziness leads to a fall and consequent fracture, all three events should be reported separately on the eCRF.
- If neutropenia is accompanied by an infection, both events should be reported separately on the eCRF.

All adverse events should be recorded separately on the Adverse Event eCRF if it is unclear as to whether the events are associated.

5.3.5.3 Persistent or Recurrent Adverse Events

A persistent adverse event is one that extends continuously, without resolution, between patient evaluation timepoints. Such events should only be recorded once on the Adverse Event eCRF. The initial severity (intensity or grade) of the event will be recorded at the time the event is first reported. If a persistent adverse event becomes more severe, the most extreme severity should also be recorded on the Adverse Event eCRF. If the event becomes serious, it should be reported to the Sponsor immediately (i.e., no more than 24 hours after learning that the event became serious; see [Section 5.4.2](#) for reporting instructions). The Adverse Event eCRF should be updated by changing the event from "non-serious" to "serious," providing the date that the event became serious, and completing all data fields related to serious adverse events.

A recurrent adverse event is one that resolves between patient evaluation timepoints and subsequently recurs. Each recurrence of an adverse event should be recorded as a separate event on the Adverse Event eCRF.

Pirfenidone—F. Hoffmann-La Roche Ltd

124/Protocol ML39355, Version 2 dated 09-Jun-2018

5.3.5.4 Abnormal Laboratory Values

Not every laboratory abnormality qualifies as an adverse event. A laboratory test result must be reported as an adverse event if it meets any of the following criteria:

- Is accompanied by clinical symptoms
- Results in a change in study treatment (e.g., dosage modification, treatment interruption, or treatment discontinuation)
- Results in a medical intervention (e.g., potassium supplementation for hypokalemia) or a change in concomitant therapy
- Is clinically significant in the investigator's judgment

It is the investigator's responsibility to review all laboratory findings. Medical and scientific judgment should be exercised in deciding whether an isolated laboratory abnormality should be classified as an adverse event.

If a clinically significant laboratory abnormality is a sign of a disease or syndrome (e.g., alkaline phosphatase and bilirubin $5 \times$ ULN associated with cholestasis), only the diagnosis (i.e., cholestasis) should be recorded on the Adverse Event eCRF.

If a clinically significant laboratory abnormality is not a sign of a disease or syndrome, the abnormality itself should be recorded on the Adverse Event eCRF, along with a descriptor indicating whether the test result is above or below the normal range (e.g., "elevated potassium," as opposed to "abnormal potassium"). If the laboratory abnormality can be characterized by a precise clinical term per standard definitions, the clinical term should be recorded as the adverse event. For example, an elevated serum potassium level of 7.0 mEq/L should be recorded as "hyperkalemia."

Observations of the same clinically significant laboratory abnormality from visit to visit should only be recorded once on the Adverse Event eCRF (see [Section 5.3.5.3](#) for details on recording persistent adverse events).

5.3.5.5 Abnormal Vital Sign Values

Not every vital sign abnormality qualifies as an adverse event. A vital sign result must be reported as an adverse event if it meets any of the following criteria:

- Is accompanied by clinical symptoms
- Results in a change in study treatment (e.g., dosage modification, treatment interruption, or treatment discontinuation)
- Results in a medical intervention or a change in concomitant therapy
- Is clinically significant in the investigator's judgment

Pirfenidone—F. Hoffmann-La Roche Ltd

It is the investigator's responsibility to review all vital sign findings. Medical and scientific judgment should be exercised in deciding whether an isolated vital sign abnormality should be classified as an adverse event.

If a clinically significant vital sign abnormality is a sign of a disease or syndrome (e.g., high blood pressure), only the diagnosis (i.e., hypertension) should be recorded on the Adverse Event eCRF.

Observations of the same clinically significant vital sign abnormality from visit to visit should only be recorded once on the Adverse Event eCRF (see [Section 5.3.5.3](#) for details on recording persistent adverse events).

5.3.5.6 Abnormal Liver Function Tests

The finding of an elevated ALT or AST ($>3 \times \text{ULN}$) in combination with either an elevated total bilirubin ($>2 \times \text{ULN}$) or clinical jaundice in the absence of cholestasis or other causes of hyperbilirubinemia is considered to be an indicator of severe liver injury (as defined by Hy's law). Therefore, investigators must report as an adverse event the occurrence of either of the following:

- Treatment-emergent ALT or AST $>3 \times \text{ULN}$ in combination with total bilirubin $>2 \times \text{ULN}$
- Treatment-emergent ALT or AST $>3 \times \text{ULN}$ in combination with clinical jaundice

The most appropriate diagnosis or (if a diagnosis cannot be established) the abnormal laboratory values should be recorded on the Adverse Event eCRF (see [Section 5.3.5.1](#)) and reported to the Sponsor immediately (i.e., no more than 24 hours after learning of the event), either as a serious adverse event or an adverse event of special interest (see [Section 5.4.2](#)).

5.3.5.7 Deaths

All deaths that occur during the protocol-specified adverse event reporting period (see [Section 5.3.1](#)), regardless of relationship to study drug, must be recorded on the Adverse Event eCRF and immediately reported to the Sponsor (see [Section 5.4.2](#)). This includes death attributed to progression of IPF.

Death should be considered an outcome and not a distinct event. The event or condition that caused or contributed to the fatal outcome should be recorded as the single medical concept on the Adverse Event eCRF. Generally, only one such event should be reported. The term "**sudden death**" should be used only for the occurrence of an abrupt and unexpected death due to presumed cardiac causes in a patient with or without

Pirfenidone—F. Hoffmann-La Roche Ltd

preexisting heart disease, within 1 hour after the onset of acute symptoms or, in the case of an unwitnessed death, within 24 hours after the patient was last seen alive and stable. If the cause of death is unknown and cannot be ascertained at the time of reporting, "**unexplained death**" should be recorded on the Adverse Event eCRF. If the cause of death later becomes available (e.g., after autopsy), "unexplained death" should be replaced by the established cause of death.

If the death is attributed to progression of IPF, "IPF progression" should be recorded on the Adverse Event eCRF.

Deaths that occur after the adverse event reporting period should be reported as described in [Section 5.6](#).

5.3.5.8 Preexisting Medical Conditions

A preexisting medical condition is one that is present at the screening visit for this study. Such conditions should be recorded on the General Medical History and Baseline Conditions eCRF.

A preexisting medical condition should be recorded as an adverse event only if the frequency, severity, or character of the condition worsens during the study. When recording such events on the Adverse Event eCRF, it is important to convey the concept that the preexisting condition has changed by including applicable descriptors (e.g., "more frequent headaches").

5.3.5.9 Hospitalization or Prolonged Hospitalization

Any adverse event that results in hospitalization (i.e., inpatient admission to a hospital) or prolonged hospitalization should be documented and reported as a serious adverse event (per the definition of serious adverse event in [Section 5.2.2](#)), except as outlined below.

The following hospitalization scenarios are not considered to be adverse events:

- Hospitalization for respite care
- Planned hospitalization required by the protocol (e.g., to perform protocol required procedures)

- Hospitalization for a preexisting condition, provided that all of the following criteria are met:

The hospitalization was planned prior to the study or was scheduled during the study when elective surgery became necessary because of the expected normal progression of the disease

The patient has not experienced an adverse event

The following hospitalization scenarios are not considered to be serious adverse events, but should be reported as adverse events instead:

- Hospitalization that was necessary because of patient requirement for outpatient care outside of normal outpatient clinic operating hours
- Cases when medical aid was provided to the patient in the hospital reception ward

5.3.5.10 Adverse Events Associated with an Overdose or Error in Drug Administration

An overdose is the accidental or intentional use of a drug in an amount higher than the dose being studied. An overdose or incorrect administration of study treatment is not itself an adverse event, but it may result in an adverse event. All adverse events associated with an overdose or incorrect administration of study drug should be recorded on the Adverse Event eCRF. If the associated adverse event fulfills seriousness criteria, the event should be reported to the Sponsor immediately (i.e., no more than 24 hours after learning of the event; see [Section 5.4.2](#)).

There is limited clinical experience with pirfenidone overdose. Multiple doses of pirfenidone up to a dose of 4806 mg/day were administered as six 267 mg capsules three times daily to healthy adult volunteers over a 12-day dose escalation period. Adverse reactions were mild, transient, and consistent with the most frequently reported adverse reactions for pirfenidone (Esbriet EMA 2010).

5.3.5.11 Patient-Reported Outcome Data

Adverse event reports will not be derived from PRO data by the Sponsor, and safety analyses will not be performed using PRO data. However, if any PRO responses suggestive of a possible adverse event are identified during site review of the PRO data, the investigator will determine whether the criteria for an adverse event have been met and, if so, will report the event on the Adverse Event eCRF.

Pirfenidone—F. Hoffmann-La Roche Ltd

128/Protocol ML39355, Version 2 dated 09-Jun-2018

5.4 IMMEDIATE REPORTING REQUIREMENTS FROM INVESTIGATOR TO SPONSOR

Certain events require immediate reporting to allow the Sponsor to take appropriate measures to address potential new risks in a clinical trial. The investigator must report such events to the Sponsor immediately; under no circumstances should reporting take place more than 24 hours after the investigator learns of the event. The following is a list of events that the investigator must report to the Sponsor within 24 hours after learning of the event, regardless of relationship to study drug:

- Serious adverse events (see [Section 5.4.2](#) for further details)
- Adverse events of special interest (see [Section 5.4.2](#) for further details)
- Pregnancies (see [Section 5.4.3](#) for further details)

The investigator must report new significant follow-up information for these events to the Sponsor immediately (i.e., no more than 24 hours after becoming aware of the information). New significant information includes the following:

- New signs or symptoms or a change in the diagnosis
- Significant new diagnostic test results
- Change in causality based on new information
- Change in the event's outcome, including recovery
- Additional narrative information on the clinical course of the event

Investigators must also comply with local requirements for reporting serious adverse events to the local health authority and IRB/EC.

5.4.2 Reporting Requirements for Serious Adverse Events and Adverse Events of Special Interest

5.4.2.1 Events That Occur prior to Study Drug Initiation

After informed consent has been obtained but prior to initiation of study drug, only serious adverse events caused by a protocol-mandated intervention should be reported. The Serious Adverse Event/Adverse Event of Special Interest Reporting Form provided to investigators should be completed and submitted to the Sponsor or its designee immediately (i.e., no more than 24 hours after learning of the event), either by faxing or by scanning and emailing the form using the fax number or email address provided to investigators.

5.4.2.2 Events That Occur after Study Drug Initiation

After initiation of study drug, serious adverse events and adverse events of special interest will be reported until 28 days after the last dose of study drug (including rollover study). Investigators should record all case details that can be gathered immediately (i.e., within 24 hours after learning of the event) on the Adverse Event eCRF and submit the report via the electronic data capture (EDC) system. A report will be generated and sent to Roche Safety Risk Management by the EDC system.

In the event that the EDC system is unavailable, the Serious Adverse Event/Adverse Event of Special Interest Reporting Form provided to investigators should be completed and submitted to the Sponsor or its designee immediately (i.e., no more than 24 hours after learning of the event), either by faxing or by scanning and emailing the form using the fax number or email address provided to investigators. Once the EDC system is available, all information will need to be entered and submitted via the EDC system.

Instructions for reporting serious adverse events that occur > 28 days after the last dose of study treatment are provided in [Section 5.6](#).

Pirfenidone—F. Hoffmann-La Roche Ltd

130/Protocol ML39355, Version 2 dated 09-Jun-2018

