5.3.1 Adverse Event Reporting Period

Investigators will seek information on adverse events at each patient contact. All adverse events, whether reported by the patient or noted by study personnel, will be recorded in the patient's medical record and on the Adverse Event eCRF.

After informed consent has been obtained **but prior to initiation of study drug**, only serious adverse events caused by a protocol-mandated intervention should be reported (see [Section 5.4.2](#) for instructions for reporting serious adverse events).

After initiation of study drug, all adverse events will be reported until 28 days after the last dose of study drug.

For patients continuing in the rollover part of the study adverse events will be reported until Week 52.

Pirfenidone—F. Hoffmann-La Roche Ltd

120/Protocol ML39355, Version 2 dated 09-Jun-2018

Instructions for reporting adverse events that occur after the adverse event reporting period are provided in [Section 5.6](#).

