5.6 ADVERSE EVENTS THAT OCCUR AFTER THE ADVERSE EVENT REPORTING PERIOD

The Sponsor should be notified if the investigator becomes aware of any serious adverse event that occurs after the end of the adverse event reporting period (defined as 28 days after the last dose of study drug), if the event is believed to be related to prior study drug treatment. These events should be reported through use of the Adverse Event eCRF. However, if the EDC system is not available, the investigator should report these events directly to the Sponsor or its designee, either by faxing or by scanning and

Pirfenidone—F. Hoffmann-La Roche Ltd

emailing the Serious Adverse Event/Adverse Event of Special Interest Reporting Form using the fax number or email address provided to investigators.

5.7 EXPEDITED REPORTING TO HEALTH AUTHORITIES, INVESTIGATORS, INSTITUTIONAL REVIEW BOARDS, AND ETHICS COMMITTEES

The Sponsor will promptly evaluate all serious adverse events and adverse events of special interest against cumulative product experience to identify and expeditiously communicate possible new safety findings to investigators, IRBs, ECs, and applicable health authorities based on applicable legislation.

To determine reporting requirements for single adverse event cases, the Sponsor will assess the expectedness of these events using the following reference documents:

- Pirfenidone *Local Instruction for Use*
- Pirfenidone Core Data Sheet

The Sponsor will compare the severity of each event and the cumulative event frequency reported for the study with the severity and frequency reported in the applicable reference document.

Reporting requirements will also be based on the investigator's assessment of causality and seriousness, with allowance for upgrading by the Sponsor as needed.

Additionally, the IDMC will conduct regular review of the trial safety data, as described in [Section 5.2.3.2](#).

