Appendix 1 Schedule of Activities (cont.)

¹⁵ Schedule of calls in IPF Care Program you can see in Appendix 7

¹⁶ Only in patients continuing treatment with pirfenidone in real clinical practice.

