9.2. Adverse Events

eCRF form: “ADVERSE EVENTS”.

AEs will be reported on a per-patient basis, i.e. counting patients rather than events.

After informed consent has been obtained but prior to initiation of study drug, only serious adverse events caused by a protocol-mandated intervention should be reported.

After initiation of study drug, all adverse events will be reported until 28 days after the last dose of study drug. Additionally, for patients continuing in the rollover part of the study adverse events will be reported until Week 52.

Only treatment emergent AEs will be summarized. In the listings, however, all occurrences of the AEs will be presented. Treatment emergent AEs will be summarized per primary SOC and PT. Severity of treatment emergent AEs will be summarized separately.

Treatment-emergent AE is any reported adverse event that starts after initiation of the study therapy and up to 28 days after the last dose of study therapy.

All registered AEs will be coded using the MedDRA version 22.0 (or further updating) and tabulated in the report with grouping by primary system organ class (SOC) and preferred term (PT).

Number (percentage) of patients and number of AEs will be presented for the Treated Set in the following tables:

- All treatment-emergent AE / SAE;
- Treatment-emergent AE / SAE related to the study drug (“Is the adverse event suspected to be caused by the study drug on the basis of facts, evidence, science-based rationales, and clinical judgment?” = “Yes” including those events where assessment is missing);
- TEAE by maximum severity (Severity, CTCAE v.4.0);
- TEAE related to study drug by maximum severity (Severity, CTCAE v.4.0);
- TEAE leading to the permanent discontinuation of study drug (Action taken with IMP=“Permanently discontinued”);
- TEAE leading to death (AE with Outcome = “Death”) including TEAE related to the study drug;
- TEAE related to the study drug leading to death;
- TEAE of special interest (“Is this an adverse event of special interest?” = “Yes”);
- Non-serious TEAEs that occurred at a frequency of $\geq 5\%$ (if no events occurred at the 5% threshold all non-serious TEAEs will be tabulated).

ML39355_STATISTICAL ANALYSIS PLAN_Final 2.0_17 June 2020

This set of tables will be repeated for the following study periods:

- Treatment period defined as first dose of study drug to last dose of study drug in the treatment period + 28 days or until the first dose in the rollover period (Treated Set).

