- Rollover period defined as first dose in the rollover to last dose in the rollover study + 28 days (Treated Set, patient continuing in the rollover study).

Tables of TEAEs by maximum severity will be prepared using the following rules: each SOC / PT category will include only the AEs with the worst severity for each patient. In the Overall category, all AEs of the patient will be presented. Each patient will be counted only once with the worst severity in each SOC and each PT level as well as in the Overall level.

Number of patients who died will be tabulated.

All AEs/SAEs will be listed. Non-treatment emergent adverse events will be identified accordingly in the listing.

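### For rollover patients, Protocol 5.3.1 ends adverse event reporting at Week 52 while 5.4.2.2 and 5.6 end serious event reporting 28 days after the last dose; the two rules, and the two SAP windows for rollover exacerbations, need reconciling.

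*Protocol*

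**What the plan says.** **Adverse events.** Protocol 5.3.1 sets a general rule: "After initiation of study drug, all adverse events will be reported until 28 days after the last dose of study drug". It then adds a fixed end for one group: "For patients continuing in the rollover part of the study adverse events will be reported until Week 52".

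**Serious events and AESIs.** Protocol 5.4.2.2 says these "will be reported until 28 days after the last dose of study drug (including rollover study"), and sends later serious events to 5.6. There the reporting period is "defined as 28 days after the last dose of study drug), if the event is believed to be related to prior study drug treatment". Section 5.6 does not mention Week 52.

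**Deaths.** Protocol 5.3.5.7 requires every death in the 5.3.1 reporting period to be recorded and reported immediately, whatever its relationship to drug.

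**SAP collection and counting.** SAP 9.2 repeats the Week 52 rule: "Additionally, for patients continuing in the rollover part of the study adverse events will be reported until Week 52". It defines a treatment-emergent event (TEAE) as one starting "up to 28 days after the last dose of study therapy", and sets the analysis period as "Rollover period defined as first dose in the rollover to last dose in the rollover study + 28 days".

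**SAP exacerbations.** SAP 8.3 counts only exacerbations that led to death. It promises a long-term follow-up table running from Week 26 to Week 52, then says that the treatment and rollover periods for this analysis follow Section 9.2.

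**Who is in the rollover.** The Appendix 1 footnote on long-term follow-up reads: "Only in patients continuing treatment with pirfenidone in real clinical practice".

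**The concern.** One rule has a calendar end and the other an end tied to dosing, and no section says which governs a rollover patient. Sites could therefore apply different rules to the same kind of event. The events at risk are serious events judged unrelated that occur well after drug was stopped. A site following 5.4.2.2 and 5.6 would not send them, although 5.3.1 still asks for adverse events in that patient. Fatal events are the sharpest case, because 5.3.5.7 and 5.6 give opposite instructions.

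The exacerbation tables inherit the problem. Exacerbations are an exploratory endpoint that Protocol 3.3.5 expects to be infrequent, in a study of about 60 patients. One fatal case included or left out would visibly change the table.

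**Working it through.** There is no figure in the plan to reproduce; the check is date arithmetic on the stated rules.

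**Inputs**
- AE end for rollover patients: Week 52, nominal day 52 × 7 = 364 (Protocol 5.3.1; repeated in SAP 9.2).
- SAE and AESI end: last dose, rollover included, plus 28 days = last dose week + 4 (Protocol 5.4.2.2).
- SAP rollover window: last rollover dose + 28 days, so it ends with the SAE rule (SAP 9.2). There are three statements but two end dates.
- SAP Week 52 visit window: days 344 to 378 (SAP 7).

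**Where the rules meet.** 364 − 28 = day 336, a last dose at Week 48. At the edges of the visit window, 344 − 28 = day 316 (Week 45.1) and 378 − 28 = day 350 (Week 50.0).

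**Either side of that point**

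| Last rollover dose | AE end | SAE/AESI end and SAP window end | Difference, weeks |
|---|---|---|---|
| Week 30 | Week 52 | 30 + 4 = Week 34 | 34 − 52 = −18 |
| Week 39 | Week 52 | 39 + 4 = Week 43 | 43 − 52 = −9 |
| Week 44 | Week 52 | 44 + 4 = Week 48 | 48 − 52 = −4 |
| Week 48 | Week 52 | 48 + 4 = Week 52 | 0 |
| Week 52 | Week 52 | 52 + 4 = Week 56 | 56 − 52 = +4 |

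**Early stop.** Take a last rollover dose at Week 30 and an event at Week 40.
- Non-serious event: due under 5.3.1.
- Non-fatal SAE judged unrelated: due under 5.3.1, since an SAE is an adverse event (5.2.2); not due under 5.4.2.2, whose period ended at Week 34, nor under 5.6.
- Unrelated death: immediately reportable under 5.3.5.7, which points to 5.3.1; not required under 5.6.
- SAE believed related: notifiable under 5.6 in any case.

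**Still on drug at Week 52.** Non-serious collection stops at Week 52. The SAE rule and the SAP window run to last dose + 28 days, so at least to Week 56. The schedule in Appendix 1 has no contact after the Week 52 visit (± 2 weeks).

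**Exacerbations.** Take a last rollover dose at Week 30 and a fatal exacerbation at Week 40. It lies between Weeks 26 and 52, so the first SAP 8.3 definition counts it. It lies after Week 34, so the Section 9.2 window does not. Tables 2.18 and 2.19 could come out either way.

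**The case against.** The strongest reply is that serious events are adverse events. Section 5.3 requires every adverse event to be recorded with its seriousness, 5.2.2 and 5.4 require SAEs within 24 hours without naming an end date, and 5.3.5.7 carries deaths through the 5.3.1 period. On that reading nothing serious lapses before Week 52. This stands against any claim that serious events definitely have the shorter period. It does not remove the conflict: 5.4.2.2 names the rollover explicitly and gives a different end, and 5.6 relies on that end to narrow what must be sent.

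Second, the early-stop case assumes that a patient who stops drug remains in the rollover. The Appendix 1 footnote suggests otherwise. The SAP, however, expects such stops: Table 3.11.2 covers events leading to discontinuation during the rollover, and Listing 26 has an end date and reason for stopping. The documents leave the patient's status open, so the case is conditional.

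Third, collection and treatment-emergence periods serve different purposes and need not match. That is right, and SAP 9.2 still lists events outside the TEAE window. The SAP window is not a third reporting deadline.

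A reader might infer more, without support:
- *A gap of up to 22 weeks.* That needs a last dose at Week 26 (52 − 30 = 22), but such a patient took no rollover dose. It is a limit, not a case.
- *No data after Week 52.* SAEs and AESIs remain reportable; only non-serious collection and scheduled contact stop.
- *Rollover tables that treat later time as observed.* They give patient and event counts with no person-time, so the longer window inflates no denominator. The effect is uneven ascertainment.

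**Conclusion.** The inconsistency is real and should be corrected; its consequences are bounded. For rollover patients, 5.3.1 cannot be followed together with 5.4.2.2 and 5.6 unless the last dose falls at about Week 48 (Week 45.1 to 50.0 across the SAP visit window). With an earlier stop, the doubt concerns unrelated SAEs more than 28 days after the last dose: 18 weeks for a stop at Week 30, 9 weeks for a stop at Week 39. This rests on such patients still counting as in the rollover. For deaths, 5.3.5.7 and 5.6 conflict on the same assumption. For patients on drug at Week 52, the TEAE window extends at least 4 weeks beyond non-serious collection, so late counts hold serious events and AESIs only.

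The two exacerbation windows in SAP 8.3 can give different counts from the same data. The primary and secondary efficacy analyses are untouched. The documents give no expected number of patients who stop during the rollover, so the number of events at stake cannot be estimated.

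One tempting remedy, ending everything at Week 52, should be avoided: it would remove the existing 28-day post-dose SAE and AESI period for every patient still on drug at that visit.

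**What to change.** **Protocol 5.3.1, 5.4.2.2 and 5.6.** State one rule for rollover patients, including those who stop drug: SAEs and AESIs are reported at least to the Week 52 visit, or to 28 days after the last dose where that is later. Use the same definition of the reporting period in 5.6, so that 5.3.5.7 and 5.6 agree on deaths. Say whether patients who stop keep the Week 39 and Week 52 visits and, if not, how their events are to be learned of.

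**SAP 9.2.** Keep the TEAE window at last dose + 28 days. Add that non-serious events are collected only to Week 52, with a footnote to the rollover tables.

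**SAP 8.3.** Use one window, Week 26 to Week 52, for the rollover exacerbation tables, and remove the cross-reference to 9.2 for that period.

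**Cost.** A few sentences in three protocol sections and two SAP sections, plus a small number of additional SAE reports from patients who stopped during the rollover. No visit beyond those already scheduled is needed. If follow-up is already complete, make the SAP changes and state in the study report which rule sites applied.
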